## 7.5 Serious Adverse Event Reporting/ Unanticipated Adverse Device Effects – Procedures for Investigators

### 7.5.1 *Initial Reports*

All SAEs/UADEs occurring from the time of informed consent until discharge from the study must be reported to Medpace Clinical Safety within 24 hours of the knowledge of the occurrence. After discharge from the study, any SAE/UADE that the Investigator considers related to study drug must be reported to the Medpace Clinical Safety or the Sponsor/designee.

To report the SAE/UADEs, complete the form electronically in the electronic data capture (EDC) system for the study. When the form is completed, Medpace Safety personnel will be notified electronically by the EDC system and will retrieve the form. If the event meets serious criteria and it is not possible to access the EDC system, send an email to Medpace Safety at [[contact]](mailto:[contact]) or call the Medpace SAE reporting line (phone number listed below), and fax/email the completed paper form to Medpace (contact information listed in Section 7.5.2) within 24 hours of awareness. When the EDC system becomes available, the SAE information must be entered as soon as possible.

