## PROTOCOL SYNOPSIS

Study title: A randomized, open-label, parallel-group study to evaluate the efficacy of the digital therapeutic OXD01 (MODIA™) in combination with sublingual buprenorphine/naloxone for the treatment of opioid use disorder.	
Study number: OXD01-001	Product: OXD01
Study phase: III	Study population: Male and female subjects
Number of subjects: 510 enrolled (approximately), 400 randomized	Number of study centers: 30-35
Sponsor: Orexo US, Inc.	
Background/Rationale: Medication-assisted treatment, the current standard for opioid addiction, is the use of medications in combination with counseling and behavioral therapies to provide a “whole-patient” approach to the treatment of opioid use disorder (OUD). However, patients may not have optimal access to face-to-face clinical behavioral health services. Digital therapeutics can help bridge the gap between accessible services and optimal treatment of OUD, the primary goal of which is to reduce the use of opioids. OXD01 is a device-based digital therapeutic, designed to offer individuals diagnosed with OUD quality psychotherapy intervention based on cognitive behavioral therapy and motivational interviewing. This study is being conducted to determine the value of OXD01 when combined with medication to change opioid use patterns in subjects with OUD.	
Objectives: Primary Objective:  The primary objective of the study is to determine whether the combination of sublingual (SL) buprenorphine/naloxone (BUP/NAL) standard of care (SOC) background therapy and the digital therapeutic OXD01 is superior to SL BUP/NAL alone to reduce opioid use, as measured by the treatment success rate. Treatment success is defined as the subject having $\geq 80\%$ of urine drug tests negative for opioids plus negative self-reports for illicit opioid use (from the TLFB interview at the same visit) from Week 6 to Week 25.	

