#### ***3.1.2 Study Treatments***

On study Day 1, subjects stabilized on SL BUP/NAL SOC background therapy will be randomized to SL BUP/NAL alone, or to SL BUP/NAL plus the OXD01 digital therapeutic. A stabilized subject will have completed SL BUP/NAL induction, with physical withdrawal symptoms reduced so the subject is able to fully participate in OXD01 training, if randomized to that treatment group. Induction with SL BUP/NAL and titration to a maintenance dose that suppresses withdrawal signs and symptoms is described in the product information under Dosage and Administration and can be implemented in accordance with the Investigator's standard of practice. Note: No investigational product will be administered as part of this study.

Subjects randomized to SL BUP/NAL plus OXD01 will be trained to use OXD01 on Day 1 as directed in the OXD01 Clinician User Guide and will begin to access the therapeutic counseling modules for 15-30 minutes, 1-2 times per week as instructed. Randomization and OXD01 training should be conducted as soon as the subject is clinically stable, with physical withdrawal symptoms managed and the subject able to fully participate in the process, but no greater than 14 days from the first dose of SL BUP/NAL induction.

Subjects in both groups will use the assigned treatment for 24 weeks.

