### 5.2 Sublingual Buprenorphine/Naloxone Medication Assisted Treatment

The subject will obtain buprenorphine/naloxone sublingual tablets from a retail pharmacy with a prescription from the Investigator. Prior to study Day 1 subjects will initiate SL BUP/NAL, complete induction, and have physical withdrawal symptoms reduced so the subject is able to fully participate in OXD01 training, if randomized to that treatment group. Subjects will take the prescribed dose daily of SL BUP/NAL from Day 1 through Day 169 as directed by the Investigator.

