### 7.1.3 *Unanticipated Adverse Device Effect*

An unanticipated adverse device effect (UADE) is any serious adverse effect on health or safety, any life-threatening problem or death caused by, or associated with a device, if that effect, problem, or death was not previously identified in nature, severity, or degree of incidence in the device; or any other unanticipated serious problem associated with a device that relates to the safety or welfare of subjects.

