## 7.2 Adverse Event Reporting Period

The AE reporting period will start after signing the informed consent form and will end at discharge from the study.

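### The post-discharge safety reporting rule in Protocol 7.5.1 is tied to an undefined study drug, so read literally it omits serious events related only to OXD01 that begin after discharge

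*Protocol*

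**What the plan says.** Protocol 7.5.1 has two rules, divided at discharge.

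- **Up to discharge**, there is no relatedness filter: "All SAEs/UADEs occurring from the time of informed consent until discharge from the study must be reported", within 24 hours of the site learning of the event.
- **After discharge**, a filter applies: "After discharge from the study, any SAE/UADE that the Investigator considers related to study drug must be reported" to the contract safety group, or to the sponsor or its designee. This sentence gives no deadline of its own.

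Section 7.2 closes general adverse event collection at the same point: "The AE reporting period will start after signing the informed consent form and will end at discharge from the study".

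On the products, the synopsis states that "OXD01 is a device-based digital therapeutic", and 3.1.2 that "No investigational product will be administered as part of this study". BUP/NAL is background therapy; under 5.2, "The subject will obtain buprenorphine/naloxone sublingual tablets from a retail pharmacy with a prescription from the Investigator". Section 7.1.3 defines a UADE as "any serious adverse effect on health or safety, any life-threatening problem or death caused by, or associated with a device", where it was not previously identified, or another unanticipated serious problem associated with a device. For each adverse event, 7.4 asks the Investigator to judge relatedness to the medical device. It lists no item for relatedness to a drug.

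**The concern.** After discharge the duty to report depends on a causal judgement about a product, and the sentence appears to name the wrong kind of product. A UADE is device-associated by definition, so requiring it to be related to a drug before it is reportable makes little sense. The one causal judgement that 7.4 tells Investigators to record is not the one that this rule uses.

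At stake is whether the sponsor hears of a late serious effect of OXD01. Section 1.1 says that OXD01 has not been studied in patients receiving this background medication. Section 7.6 has the sponsor report UADEs to the FDA, which it can do only for events that sites have passed on. With 30-35 centers planned, sites may read the term differently.

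**Working it through.** This is a question of wording, so no formula applies and the plan gives no figure to reproduce. The check is to list what *study drug* could mean, apply each meaning to each kind of event, and see whether another section fills any gap.

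**Step 1: possible meanings.** The documents do not define the term.

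- *Meaning A, an investigational drug.* Section 3.1.2 says that none is administered, and the same note appears in the synopsis, in Sections 3 and 5.1, and in SAP 2.2.3. The trigger would then cover nothing.
- *Meaning B, BUP/NAL.* Subjects in both groups take it, 9.4 speaks of study medication, and 13.2 speaks of study drug accountability. This is the only drug the term could denote.

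OXD01 is a web-based device and fits neither meaning. The protocol does have a wider term, study treatment, which is used in 4.4 for relatedness and as the title of Section 5, where OXD01 is included. Section 7.5.1 does not use it.

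**Step 2: apply them.**

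| Serious event | Reportable under meaning A | Reportable under meaning B |
|---|---|---|
| Occurs before discharge, known before discharge | Yes | Yes |
| Occurs before discharge, learned of later | Yes | Yes |
| Onset after discharge, related to BUP/NAL | No | Yes |
| Onset after discharge, related only to OXD01 | No | No |

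The first two rows follow from the pre-discharge sentence: it turns on when the event occurred, and its 24-hour clock runs from knowledge. The last row is negative whichever meaning is taken.

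**Step 3: look for another rule that covers the last row.**

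- 7.2 ends adverse event reporting at discharge.
- 7.5.2 governs follow-up of SAEs/UADEs. It does not say which new post-discharge events are to be reported.
- 7.6 assigns onward reporting by the sponsor and the contract organization, which presupposes a site report.
- 7.7 follows pregnancy outcomes even after discontinuation and treats congenital abnormalities and spontaneous miscarriages as SAEs. This is a real exception, but it is confined to pregnancy.

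No section sets a general Investigator duty to report serious OXD01-related events with onset after discharge.

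**The case against.** The best defence is that the intent is plain. The sentence itself names UADEs, the section title does too, and 7.4 directs Investigators to judge relatedness to the device. Only a reading that empties UADE of meaning excludes OXD01, and many Investigators would report such an event anyway. This stands as evidence of intent: the phrase looks like template carry-over, not a deliberate exclusion. It does not repair the text, because a reporting duty should not rest on each site inferring what was meant.

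The likely yield is also small. Section 8.1.1 calls OXD01 non-systemic with a low likelihood of adverse events and lists disappointment, distress and frustration. Assigned use ends at Day 169. This stands too and limits the weight of the point.

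Three stronger readings are tempting, and the documents do not support them.

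- *Any device event learned of after discharge is lost.* It is not. If it occurred before discharge, the pre-discharge sentence covers it.
- *The trial has no study drug at all.* The documents say only that no investigational product is administered. Subjects do take BUP/NAL, so the term is undefined but not necessarily empty.
- *The study-level safety triggers in 4.5 are undermined.* Of the three listed there, the trigger for an unexpected OXD01-related SAE and the one for other significant risks refer expressly to events or risks in the study, and events up to discharge are reported without a relatedness filter. Nothing shows that the triggers depend on events with onset after discharge.

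**Conclusion.** The point holds in a limited form. Followed literally, 7.5.1 requires no report of a serious event related only to OXD01 that begins after discharge, and it conflicts with the device-based definitions in 7.1.3 and 7.4. It is an inconsistency in an operative safety rule and is worth correcting for that reason.

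The number of events affected cannot be derived from the documents and is probably small. The primary endpoint, alpha, power, sample size and efficacy analysis are unaffected. The conclusion rests on a literal reading of *study drug* and on there being no other reporting instruction outside these documents, such as a site safety manual. Discharge is not defined either. If it means Week 25 or early termination, the gap opens earlier for subjects who leave early, possibly while others are still using OXD01.

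**What to change.** In Protocol 7.5.1, replace *related to study drug* with *related to the medical device (OXD01)*. That brings the post-discharge trigger into line with the UADE definition in 7.1.3 and the causality item in 7.4.

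Whether late SAEs related to SL BUP/NAL should also be reported is a separate decision for the sponsor. Sections 7.1.3 and 7.4 do not call for it, but 7.6 forwards BUP/NAL-related SAEs to the manufacturer, and SAP 3.5.1 tabulates adverse events related to the background therapy. If the sponsor intends it, name SL BUP/NAL in the same sentence. The same edit can state a reporting deadline, which the sentence now lacks.

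The cost is one sentence in an amendment and a short site training note. No new procedure or data collection is needed.

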### 7.5.2 *Follow-up Reports*

The Investigator must continue to follow the patient until the SAE/UADE has subsided or until the condition becomes chronic in nature, stabilizes (in the case of persistent impairment), or the patient dies.

Within 24 hours of receipt of follow-up information, the Investigator must update the form electronically in the EDC system for the study and submit any supporting documentation (e.g., patient discharge summary or autopsy reports) to Medpace Clinical Safety via fax or e-mail. If it is not possible to access the EDC system, refer to the procedures outlined above for initial reporting of SAEs/UADEs.

Safety Contact Information: Medpace Clinical Safety

Medpace SAE reporting line:

[contact], dial 3 or [contact], dial 3

[contact] or [contact]

E-mail: [[contact]](mailto:[contact])

The Investigator is primarily responsible for ensuring proper care of study subjects. Medical queries with regards to the management of subjects with SAEs and AEs may also be addressed to the medical monitor at Orexo.

## **7.6 Reporting Responsibilities**

Orexo will report UADEs to the FDA. Medpace will be responsible for submitting reports of UADEs to sites and Central IRBs according to applicable regulations and stipulated timelines. Sites will be responsible for reporting to local IRBs as required.

In the event an SAE is reported as related to BUP/NAL (SOC background therapy), Medpace will forward this information to the manufacturer for postmarketing reporting to the FDA as required.

## **7.7 Pregnancy**

A confirmed pregnancy does not require withdrawal of the subject from the study. The Investigator should consider the risk-benefit analysis for the individual subject and either continue or discontinue BUP/NAL treatment based on their clinical judgement.

The outcome of all pregnancies (spontaneous miscarriage, elective termination, normal birth or congenital abnormality) must be followed up and documented even after the subject was discontinued from the trial.

All events of congenital abnormalities/birth defects are SAEs. Spontaneous miscarriages should also be reported and handled as SAEs.

## **8. MEDICAL SAFETY**

### **8.1 Expected Side Effects**

#### **8.1.1 OXD01**

Since OXD01 is a non-systemic therapy for OUD, the likelihood of adverse events is low. However, the following emotions may occur when using the application:

- Disappointment if there is no benefit
- Distress when presented with particular topics.
- Frustration, or other distressing emotions, if the content is found to be confusing, overwhelming, or unsuitable.

Subjects should be directed to contact the Investigator if any of these feelings become significant.

## **9. STUDY DOCUMENTS, RECORD KEEPING, SOURCE DATA AND CASE REPORT FORMS**

### **9.1 Protocol and Informed Consent Form**

The study will be performed in accordance with this study protocol. The Investigator indicated on Form FDA 1572 will act as the Principal Investigator. Copies of the signed Form FDA 1572 and protocol will be provided to the sponsor.

Based on the study protocol, Medpace will develop a written ICF that includes all of the relevant elements

currently required by FDA (21 CFR part 50) or state regulations (see section 6.1).

The protocol and the ICF must be approved by the relevant IRB prior to study conduct per 21 CFR part 56.

#### **9.2 Protocol and Informed Consent Changes**

Changes to the protocol or the ICF will be implemented as amendments to the original document and must be approved by the applicable IRB prior to implementation. Protocol amendments are normally agreed between Orexo and the Investigator prior to finalization, however, urgent changes needed to protect the safety of study subjects should be implemented directly and the sponsor and IRB should then be notified as soon as possible. Copies of all protocol and ICF amendments/revisions, along with letters noting IRB approval, will be submitted to the sponsor. Any addendum, amendment, or revision that substantially alters the study design or increases potential risk to the subject requires the subject's consent to continue in the study.

#### **9.3 Records**

Adequate records will be maintained for the study as required by International Conference on Harmonisation (ICH) Good Clinical Practices (GCP). This will include volunteer medical records, CRFs, laboratory reports, work sheets, signed ICFs, drug dispensing records, AE reports, information regarding volunteers' discontinuation and similar.

Following completion of the study, Medpace will supply the sponsor with originals of the CRFs (or a copy if electronic CRFs are used) and copies of laboratory reports and ECGs. CRF copies and original laboratory reports and ECGs will be retained for archiving by Medpace. No study related essential documents, records or data should be destroyed without prior written authorization by Orexo.

#### **9.4 Source Data and Case Report Forms**

Subjects will be identified by screening number prior to randomization and a subject number after the first dose of study medication. Source documents will be used to record all study-related data.

Source document entries will be used to complete CRFs. A set of CRFs will be completed for each subject randomized in the study. All data and CRFs will be reviewed, evaluated, and signed by the Investigator, as required. An electronic CRF (eCRF) system will be used in this study.

All changes to the eCRF data will be traced by an audit trail incorporated in the eCRF system.

### **10. DATA MANAGEMENT**

Each investigative site will maintain source documentation and enter subject data into the CRFs as accurately as possible and will respond to any reported discrepancies rapidly.

Electronic case report forms are accessed at the investigative sites. This electronic data capture system is validated and compliant with US Title 21 CFR Part 11. Each person involved with the study will have an individual identification code and password that allows for record traceability. Thus, the system, and subsequently any investigative reviews, can identify coordinators, Investigators, and individuals who have entered or modified records, as well as the time and date of any modifications. There is an internal quality review audit of the data

and additional reviews by a clinical monitor.

Each CRF is presented as an electronic copy, allowing data entry by clinical unit personnel, who can add and edit data, add new subjects, identify and resolve discrepancies, and view records. This system provides immediate direct data transfer to the database, as well as immediate detection of discrepancies, enabling clinical unit personnel to resolve and manage discrepancies in a timely manner.

Paper copies of the CRFs and other database reports may be printed and signed by the Investigator. This system provides clinical unit personnel, monitors, and reviewers with access to hardcopy audits, discrepancy reviews, and Investigator comment information.

## **11. STATISTICAL CONSIDERATIONS AND DETERMINATION OF SAMPLE SIZE**

Prior to the database lock, a detailed statistical analysis plan will be completed and placed on file. The statistical analysis plan will contain a more comprehensive explanation of the methodology used in the statistical analyses than that described below. The statistical analysis plan will also contain the rules and data handling conventions used to perform the analyses, and the procedure used for accounting for missing data.

In general, summary tabulations will display the number of observations, mean, standard deviation, median, minimum, maximum, and appropriate percentiles for continuous variables, and the number and percentage by category for categorical data. Summaries will present data by treatment arm and overall. The data listings will include all available efficacy and safety data.

### **11.1 Study Populations**

The primary efficacy analyses will be based on full analysis population that consists of all randomized subjects. The safety analyses will be based on safety population that is consistent of all randomized subjects.

### **11.2 Study Disposition**

Demographic and baseline characteristics for the enrolled subjects will be summarized separately by treatment assignment. Summary statistics will be used to describe these two groups. No hypotheses will be tested with respect to baseline characteristics.

### **11.3 Primary Objective**

The primary objective of the study is to determine whether the combination of SL BUP/NAL SOC background therapy and the digital therapeutic OXD01 is superior to SL BUP/NAL alone to reduce opioid use, as measured by the treatment success rate. Treatment success is defined as the subject having  $\geq 80\%$  of urine drug tests negative for opioids plus  $\geq 80\%$  of self-reports negative for illicit opioid use (from the TLFB interview at the same visit) from Week 6 to Week 25. Each subject will be evaluated as a success or failure for this metric and the proportion of subjects in each group demonstrating  $\geq 80\%$  of urine drug tests negative for opioids plus negative self-reports for illicit opioid use (from the TLFB interview) will be tested using chi-squared test.

#### 11.4 Secondary Objectives

The secondary objectives are to determine whether the combination of SL BUP/NAL SOC background therapy and the digital therapeutic OXD01 is superior to SL BUP/NAL alone with respect to the following variables. Note that the secondary objectives are listed in priority order for potential gatekeeping statistical approaches.

- Cumulative response – The cumulative response rate from Week 6 to Week 25 of treatment. Response is defined as the presence of both a negative urine drug test for opioids and a self-report negative for illicit use of opioids at a study visit.

To compare the two treatment groups with respect to their cumulative distribution functions of the proportion of subjects responding, the Kolmogorov-Smirnoff methodology will be used.

- Illicit use of opioids - The cumulative response rate from Week 6 to Week 25 of treatment with respect to the percentage of urine drug tests negative for opioids will be the primary metric for this variable. To compare the two treatment groups with respect to their cumulative distribution functions of the proportion of subjects responding, the Kolmogorov-Smirnoff methodology will be used.
- Self-reports of illicit use of opioids - The cumulative response rate from Week 6 to Week 25 of treatment with respect to the percentage of self-reports negative for illicit use of opioids will be the primary metric for this variable. To compare the two treatment groups with respect to their cumulative distribution functions of the proportion of subjects responding with self-reports negative for illicit opioid use, the Kolmogorov-Smirnoff methodology will be used.
- Percentage of subjects abstinent - Abstinence is defined as a subject having urine drug tests negative for opioids as well as self-reports negative for illicit use of opioids at Week 25. Each subject will be scored as abstinent or non-abstinent and the groups will be compared using a chi-squared test.
- Proportion of subjects completing the study - A completer is defined as a participant who completed either the UDS or the self-report assessment at the Week 25 visit. The groups will be compared with respect to the proportion of completers using a chi-squared test.
- Clinical global impression - This will be evaluated in two ways.
  - Score on the CGI-I scale at week 12 and Week 25
  - Change from baseline in the Clinical Global Impression-Severity score at Week 12 and Week 25

CGI scores will be evaluated using general linear model methodology or non-parametric analogs.

- Opioid cravings - Change from baseline in the opioid craving score using the Opioid Craving VAS from Week 4 to Week 25. Opioid Craving scores will be evaluated using general linear model methodology or non-parametric analogs.
- Use of illicit non-opioid drugs of abuse - The cumulative percentage of subjects with urine drug tests negative for illicit drugs of abuse (excluding opioids) plus self-reports negative for illicit drug use for the period from Week 6 to Week 25 will be evaluated using the Kolmogorov-Smirnoff methodology.

- Number of hospitalizations, emergency department visits, and overdoses, and the ability to resume work, school, or other productive activity.

